10.8.2.3. Duration of Stable Disease

Duration of stable disease (DoSD) is defined as the time, in days, from the first date of treatment until the first date at which PD is experienced or the subject dies due to underlying cancer.

The duration will be calculated (in days) as:

Date of first overall response of PD or date of death from underlying cancer (whichever is first)
– Date of first treatment.

The duration of stable disease will be summarised by cohort using descriptive summaries, which will not account for censoring. Additionally, Kaplan-Meier curves will be produced for each cohort along with a table summarising the median and 25th and 75th percentiles of the duration of stable disease, inclusive of censoring, for each cohort, including sub-cohort.

[Kaplan-Meier plot: y-axis = cumulative proportion of participants who still have stable disease, x-axis = day, one line for each cohort, including sub-cohort, overlayed on the same plot].

Censoring

If a subject does not experience PD or death due to underlying cancer their duration will be censored at the date of their last disease assessment.

If a subject dies due to a cause other than underlying cancer they will be censored at the date of death.

If a subject does not have a disease assessment after their first treatment they will be censored at the date of their first treatment.

If a subject initiates another cancer treatment prior to PD/death their duration of stable disease will be censored at the last assessment prior to initiation of the alternative cancer treatment.

If a subject experiences PD or death immediately following 2 or more visits at which their response was missing or NE their duration of stable disease will be censored at the time of their last assessment prior to missing/NE response.

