9.3.1. Efficacy Analyses

Efficacy analyses will be performed separately for each cohort. RECIST 1.1 criteria will be used for the primary endpoint evaluation ([Eisenhauer et al., 2009](#)), and iRECIST will be used for the exploratory endpoint response evaluation ([Seymour et al., 2017](#)). The iRECIST endpoints are analyzed using the same statistical methodology and the results will be presented in the same ways for the corresponding RECIST 1.1 endpoints.

The primary efficacy endpoint is the ORR defined as the proportion of subjects who achieve confirmed CR or PR per RECIST v1.1. The best overall response is the best response recorded from the start of the treatment until PD. The smallest measurements recorded since the treatment started will be used as the reference for PD. Subjects with CR or PR are considered to have obtained objective response. Subjects with not-evaluable response (NE) are counted as non-responders. Exact 95% CI will be constructed for the ORR for each cohort.

Subjects with CR, PR or SD are considered to have achieved disease control. Disease control rate is defined as the proportion of subjects who have achieved CR, PR, and SD. Duration of response only applies to subjects whose best overall response is CR or PR and is defined as the number of days from the first documentation of objective tumor response to the date of first PD or death due to underlying cancer.

Duration of stable disease is measured from the start of the treatment (the first treatment date for non-randomized studies, the randomization date for randomized studies) until the date when the criteria for overall disease progression are first met.

Duration of response is the time from first evaluation showing CR or PR (response confirmation required at subsequent tumor assessment no earlier than 4 weeks after first evaluation showing CR or PR) to the time of the first subsequent evaluation showing PD or death. Only subjects who experience a confirmed CR or PR will be analyzed for DoR. Subjects who do not experience PD or death will be censored per the censoring rules in the statistical analysis plan.

Progression-free survival is defined as the number of days from Day 1 in Cycle 1 to the first documented progression or death due to any cause. Only deaths that occurred within 30 days of the last progression assessed.

Overall survival is defined as the time from the first dose of study drug to death due to any cause.

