10.8.2.2. Duration of Response

Duration of response (DoR) is defined as the time, in days, from the first of the 2 assessments required for confirmed PR or CR to the time of the PD or death due to underlying cancer.

The duration will be calculated (in days) as:

Date of first overall response of PD or date of death due to underlying cancer (whichever is first) – Date of first of the two assessments required for confirmed CR or PR.

The duration of response will be summarised by cohort using descriptive summaries, which will not account for censoring. Additionally, Kaplan-Meier curves will be produced for each cohort along with a table summarising the median and 25th and 75th percentiles of the duration of response, inclusive of censoring, for each cohort, including sub-cohort.

[Kaplan-Meier plot: y-axis = cumulative proportion of participants who still have response, x-axis = day, one line for each cohort, including sub-cohort, overlayed on the same plot].

Exclusion

If a subject does not achieve confirmed CR or PR they will be excluded from this analysis.

Censoring

If a subject does not experience PD or death due to underlying cancer their duration will be censored at the date of their last disease assessment.

If a subject dies due to a cause other than underlying cancer they will be censored at the date of death.

If a subject does not have a disease assessment after their assessment confirming their response as CR or PR they will be censored at the date of their last disease assessment.

If a subject initiates another cancer treatment prior to PD/death their duration of response will be censored at the last assessment prior to initiation of the alternative cancer treatment.

If a subject experiences PD or death immediately following 2 or more visits at which their response was missing or NE their duration of response will be censored at the time of their last assessment prior to missing/NE response.

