13.2. List of Tables

Table Number	Table Title
14.1.1	Participant Disposition – All Subjects
14.1.2.1	Demography – Safety Analysis Set
14.1.2.2	Demography of Cohort F – Safety Analysis Set
14.1.3.1	Baseline Disease Characteristics – Safety Analysis Set
14.1.3.2	Baseline Disease Characteristics of Cohort F – Safety Analysis Set
14.1.4.1	Prior Cancer Treatments – Safety Analysis Set
14.1.4.2	Other Prior Medications – Safety Analysis Set
14.1.4.3	Concomitant Medications – Safety Analysis Set
14.1.5	Investigational Product Exposure – Safety Analysis Set
14.2.1	Response – (RECIST v1.1) – Response Evaluable Analysis Set
14.2.2.1	Duration of Response (RECIST v1.1) – Response Evaluable Analysis Set
14.2.2.2	Duration of Response (RECIST v1.1) – KM – Response Evaluable Analysis Set
14.2.3.1	Duration of Stable Disease (RECIST v1.1) – Response Evaluable Analysis Set
14.2.3.2	Duration of Stable Disease (RECIST v1.1) – KM – Response Evaluable Analysis Set
14.2.4	Response – (iRECIST) – Response Evaluable Analysis Set
14.2.5.1	Duration of Response (iRECIST) – Response Evaluable Analysis Set
14.2.5.2	Duration of Response (iRECIST) – KM – Response Evaluable Analysis Set
14.2.6.1	Duration of Stable Disease (iRECIST) – Response Evaluable Analysis Set
14.2.6.2	Duration of Stable Disease (iRECIST) – KM – Response Evaluable Analysis Set
14.2.7	Progression Free Survival (RECIST) – KM – Response Evaluable Analysis Set
14.2.8	Progression Free Survival (iRECIST) – KM – Response Evaluable Analysis Set
14.2.9	Overall Survival – KM – Response Evaluable Analysis Set
14.3.1.1	Overall Summary of Treatment Emergent Adverse Events – Safety Analysis Set

Table Number	Table Title
14.3.1.2	Treatment Emergent Adverse Events by System Organ Class and Preferred Term – Safety Analysis Set
14.3.1.3	Treatment Emergent Adverse Events by System Organ Class, Preferred Term and Severity – Safety Analysis Set
14.3.1.4.1	Treatment Emergent Adverse Events Related to Etigilimab by System Organ Class and Preferred Term – Safety Analysis Set
14.3.1.4.2	Treatment Emergent Adverse Events Related to Nivolumab by System Organ Class and Preferred Term – Safety Analysis Set
14.3.1.4.3	Treatment Emergent Adverse Events Related to Etigilimab and Nivolumab by System Organ Class and Preferred Term – Safety Analysis Set
14.3.1.4.4	Treatment Emergent Adverse Events Related to Etigilimab or Nivolumab by System Organ Class and Preferred Term – Safety Analysis Set

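### Duration of stable disease is not limited to subjects who had stable disease, so it largely repeats progression-free survival

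*SAP*

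**What the plan says.** SAP 10.8.2.3 opens: "Duration of stable disease (DoSD) is defined as the time, in days, from the first date of treatment". In full, the clock runs "from the first date of treatment until the first date at which PD is experienced or the subject dies due to underlying cancer". The section then goes to the summaries and to censoring, with no statement of who is eligible. The Kaplan-Meier axis is to read "cumulative proportion of participants who still have stable disease". One censoring rule says: "If a subject does not have a disease assessment after their first treatment they will be censored at the date of their first treatment".

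The section just before it, SAP 10.8.2.2 on duration of response (DoR), has a paragraph headed Exclusion: "If a subject does not achieve confirmed CR or PR they will be excluded from this analysis".

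Protocol 9.3.1 gives only the two ends of the interval. It says "Duration of stable disease is measured from the start of the treatment", and the interval runs "until the date when the criteria for overall disease progression are first met". Protocol Table 2 sets a 6-week minimum for a best response of SD; SAP 10.8.2.3 does not use it.

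Tables 14.2.3.1 and 14.2.3.2 report the endpoint on the Response-Evaluable set. SAP Section 9 admits to that set anyone with measurable disease who was treated and either had a post-baseline response assessment or stopped for progression within 16 weeks (plus a 2-week window). SAP 13.2 also lists iRECIST versions, Tables 14.2.6.1 and 14.2.6.2, but no section of the SAP defines them.

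**The concern.** Duration of stable disease (DoSD) is a listed secondary endpoint. Its name and its plot axis tell the reader that it shows how long stable disease lasted in subjects who had it. Without an eligibility rule, it mixes those subjects with others who never had stable disease and with responders. A cohort's median could then reflect mainly how many subjects progressed by the first scan. No planned summary table would show the duration in the subjects that the name refers to.

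**Working it through.** The plan gives no figure for this endpoint, so there is none to reproduce. The Simon error rates and power concern the response rate and are not touched.

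**Step 1: is a restriction implied?** The SAP signals restricted endpoints with an Exclusion paragraph: DoR (10.8.2.2) and DoR by iRECIST (10.8.3.2) each have one. PFS, iRECIST PFS and OS, which cover all analysed subjects, have none. DoSD has none. It also shares with PFS the rule that censors unscanned subjects at first treatment. A subject with no post-treatment scan cannot have documented SD, so that rule has no use in an SD-only analysis.

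**Step 2: who enters, and with what value?**

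| Subject in the Response-Evaluable set | Ever had SD as best response? | DoSD as written |
|---|---|---|
| PD at the first scan | No | Event at about 8 weeks |
| Stopped for progression, never scanned | No | Censored at first treatment |
| Confirmed CR or PR | No | First treatment to PD or cancer death |
| Best response SD | Yes | First treatment to PD or cancer death |

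Scans fall every 8 (±1) weeks from Cycle 1 Day 1, so the first is at about Study Day 57 (56 days by the SAP's date subtraction).

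**Step 3: comparison with RECIST PFS (SAP 10.8.3.3).** Population, start date and PD event are the same. Deaths are handled differently:
- DoSD counts a cancer death at any time and censors other deaths at the date of death.
- PFS counts death from any cause, but only within 30 days of the last tumor assessment.

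**Step 4: size, on stated assumptions.** Suppose a share f of a cohort has PD at day 57, and the rest progress exponentially after day 57 with a further median of m days. Responders are ignored. Then:
- SD-only median = 57 + m
- Unrestricted median = 57 + m × ln((1 − f)/0.5)/ln 2 if f < 0.5, and 57 if f ≥ 0.5

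For f = 0.4 and m = 112: 57 + 112 × ln(1.2)/ln 2 = 57 + 29 = 86 days, against 57 + 112 = 169 days.

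| m (days) | SD-only median | f = 20% | f = 30% | f = 40% | f ≥ 50% |
|---|---|---|---|---|---|
| 56 | 113 | 95 | 84 | 72 | 57 |
| 112 | 169 | 133 | 111 | 86 | 57 |
| 168 | 225 | 171 | 139 | 101 | 57 |

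The values of f and m are assumptions; the documents supply neither. The last column needs no assumption about m: once half the cohort has progressed by the first scan, the median is fixed there.

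**The case against.** The SAP follows the protocol's own definition, which is also unrestricted. It plans no formal hypothesis testing, and the primary endpoint is unaffected. Subject-level information is not lost: Listing 16.2.6.4.1 prints best overall response, DoSD and PFS side by side, and the swimmer plots show each subject's course. A restricted analysis has its own weakness, because it selects on a post-baseline outcome and so guarantees several progression-free weeks. All of this stands. It limits the consequence but does not make the summary tables and curves show what their titles say.

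Some apparent evidence should be set aside. The Response-Evaluable titles and the N footnote in the Kaplan-Meier shell apply equally to DoR, which is restricted. The case rests on the missing exclusion and the rule for unscanned subjects.

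Three stronger readings are tempting, and the documents do not support them.

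- **A definite size from the prior Phase 1b data (Protocol 1.2).** Median PFS there was 57.5 days, with 37.5% progression-free at 3 months and 25.0% at 6. A reader might infer an unrestricted median of about 57 days here and, from 25.0/37.5 = 67%, an SD-only median above 6 months. But that phase enrolled 10 subjects, and the intervals are wide: 14.0 to 224.0 days, 8.7 to 67.4% and 3.7 to 55.8%. All treated subjects had prior checkpoint inhibitors, whereas Cohorts A, C, F and H exclude prior anti-PD-1/PD-L1 therapy. Being progression-free at 3 months is also not a best response of SD: it may include the partial responder, and it omits SD subjects who progressed sooner.
- **Equality with PFS apart from non-cancer deaths.** This overlooks the 30-day limit. A cancer death later than that, without prior PD, is a DoSD event but not a PFS event.
- **Damage to futility decisions.** The protocol synopsis names DoSD for germ cell futility monitoring. SAP 6.3 says the evaluation took place only for the cervical and uveal cohorts and was not required for the others before the study was terminated.

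**Conclusion.** The point holds on the text. As written, DoSD is time to progression or cancer death in the whole Response-Evaluable set. The axis label is wrong for early progressors and for responders, and the result largely repeats RECIST PFS.

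No reliable size can be given. The unrestricted median sits at about day 57 whenever at least half of a cohort progresses by the first scan. With 20 to 40% early progressors and SD-only medians of 113 to 225 days, both assumed, it would be 72 to 171 days. The distortion shrinks as early progression becomes rarer. The effect is on reporting of a descriptive secondary endpoint.

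**What to change.** 1. Add to SAP 10.8.2.3: *Exclusion: only subjects whose best overall response is SD per protocol Table 2, meeting the 6-week minimum, are included.*
2. State that unconfirmed CR or PR that protocol Table 2 maps to SD are included. This is needed because Table 14.2.1 shows unconfirmed responses on rows separate from SD.
3. Delete the rule in 10.8.2.3 that censors unscanned subjects at first treatment.
4. If an SD-or-better version is wanted, show it as a separate, labelled row.
5. Define DoSD by iRECIST in the SAP text with the matching iSD rule for Tables 14.2.6.1 and 14.2.6.2, or drop those tables.

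If the SAP is already final, SAP Section 4 provides for describing the change in the clinical study report.

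The work is a short paragraph and one filter, plus the iRECIST definition if those tables stay. There are two costs. Each cohort contributes fewer subjects. The restricted median is also conditional on remaining progression-free to the SD assessment, and the table and figure should say so.

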10.8.3. Exploratory Endpoints

10.8.3.1. Objective Response Rate (iRECIST)

The same target and non-target lesions will be used to assess response as per the iRECIST criteria.

One key difference for iRECIST as compared to RECIST v1.1 is that PD has to be confirmed. As per iRECIST, the appearance of new lesions will result in immune unconfirmed progressive disease (iUPD), with immune confirmed progressive disease (iCPD) being assigned if additional new lesions appear or new lesions increase in size (≥ 5 mm for sum of new target lesions or any increase in new non-target lesions).

iCR, iPR, iSD are defined as per Table 6, with the main difference from the assignments per RECIST v1.1 being that a subject can experience iUPD prior to iCR, iPR, iSD but not iCPD, i.e. they can have progression recorded at a visit but it needs to be confirmed at the subsequent visit for the overall response to be iCPD.

Table 6: Some Examples for Assigning Timepoint Response for iRECIST

		Time Point Response		
Target lesions	Non-Target lesions	New Lesions	No Prior iUPD	Prior iUPD
iCR	iCR	No	iCR	iCR
iCR	Non-iCR/Non-iUPD	No	iPR	iPR
iPR	Non-iCR/Non-iUPD	No	iPR	iPR
iSD	Non-iCR/Non-iUPD	No	iSD	iSD
iUPD with no change OR decrease from last TP	iUPD with no change OR decrease from last TP	Yes	NA	NLs confirms iCPD if NLs were previously identified and increase in size (≥ 5 mm in SOM for NLT or any increase for NLNT) or number; If no change in NLs (size or number) from last TP, remains iUPD
iSD, iPR, iCR	iUPD	No	iUPD	Remains iUPD unless iCPD confirmed based in further increase in size of NT disease (need not meet RECIST v1.1 criteria for unequivocal PD)
iUPD	Non-iCR/Non-iUPD ; iCR	No	iUPD	Remains iUPD unless iCPD confirmed based on: further increase in SOM of at least 5 mm, otherwise remains iUPD
iUPD	iUPD	No	iUPD	Remains iUPD unless iCPD confirmed based on further increase in: 
 previously identified T lesion iUPD in SOM ≥ 5 mm and / or NT lesion iUPD (prior assessment – need not be unequivocal)
iUPD	iUPD	Yes	iUPD	Remains iUPD unless iCPD confirmed based on further increase in 
 previously identified T lesion iUPD SOM ≥ 5 mm and / or previously identified NT lesion iUPD (need not be unequivocal) and /or size or number of new lesions previously identified
Non-iUPD/PD	Non-iUPD/PD	Yes	iUPD	Remains iUPD unless iCPD confirmed based on increase in size or number of new lesions previously identified

As with RECIST v1.1, iRECIST defines confirmed iCR and iPR response as the same overall response being achieved at the subsequent visit, which should be at least 4 weeks later. The best overall

response is then the best response achieved in order of iCR, iPR, iSD, iUPD, iCPD, NE. A subject can experience iUPD prior to any response, but not iCPD.

Immune Objective Response Rate (iORR) is then defined as the proportion of subjects who achieve a best overall response of iCR or iPR (confirmed). Subjects with not-evaluable response (NE) are counted as non-responders.

The number and percentage of subjects who have achieved objective response will be summarised, by cohort, including sub-cohort, along with the 95% Clopper-Pearson CI.

Additionally the number and percentage of subjects with iCR and iPR (confirmed and unconfirmed), iSD, iUPD, iCPD and NE will be summarised by cohort, including sub-cohort.

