If repeat imaging shows iRECIST confirmed disease progression (iCPD), subjects will discontinue treatment. However, if the subject is deriving benefit after iCPD is observed, an exception to continue study treatment must be approved by the sponsor's Medical Monitor. Subjects who have repeat imaging to confirm progression are not required to undergo the next scheduled tumor imaging if it is less than 4 weeks later.

If repeat imaging shows iRECIST stable disease (iSD), iRECIST partial response (iPR), or iRECIST complete response (iCR), imaging should be continued every 8 (± 1) weeks and the subject should continue on trial treatment.

Note that the date of progression to be used for all relevant efficacy endpoints will be based on first documentation of PD (ie, RECIST v1.1 date of PD), regardless of date of confirmation of PD for subjects who continue on treatment.

All radiographic evaluations performed on the study will be collected and held for a potential independent review. Details regarding initiating an independent review will be outlined in the statistical analysis plan (SAP).

Confirmed progression of disease is defined as one of the following:

Clinical deterioration with or without radiographic PD per RECIST v1.1 (See [Appendix 7](#)) will confirm progression of disease. Note, however, that radiographic evaluation should be conducted at the time of clinical signs and/or symptoms of PD whenever possible.

- In subjects without clinical deterioration at the time of a radiographic scan showing PD per RECIST v1.1, a second scan conducted at least 4 weeks later showing progression of disease as outlined below will confirm progression:
- An additional 10% increase in tumor burden with a minimum 5 mm absolute increase from time of initial PD. This includes an increase in the sum of diameters of all target lesions and/ or the diameters of new measurable lesions compared to the time of initial PD.

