iCR = immune complete response; iPR = immune partial response; iSD = immune stable disease; iUPD = immune unconfirmed progression; iCPD = immune confirmed progression; NL = new lesion; NLT = new lesion target; NLNT = new lesion non target; T = target; TP = timepoint; NA = not applicable; NE = not evaluable / evaluated

Assigning best overall response for iRECIST

Best overall response					
TPR1	TPR2	TPR3	TPR4	TPR5	iBOR
iCR	iCR, iPR, iUPD, NE	iCR, iPR, iUPD, NE	iUPD	iCPD	iCR
iUPD	iPR, iSD, NE	iCR	iCR, iUPD, NE	iCR, iPR, iSD, iUPD, iCPD, NE	iCR
iUPD	iPR	iPR, iSD, iUPD, NE	PR, iSD, iUPD, NE, iCPD	iPR, iSD, iUPD, NE, iCPD	iPR
iUPD	iSD, NE	iPR	iPR, iSD, iUPD, NE	PR, iSD, iUPD, iCPD, NE	iPR
iUPD	iSD	iSD, iUPD, NE	iSD, iUPD, iCPD, NE	iSD, iUPD, iCPD, NE	
iUPD	iCPD	Anything	Anything	Anything	iCPD
iUPD	iUPD (no iCPD)	iCPD	Anything	Anything	iCPD
iUPD	NE	NE	NE	NE	iUPD

Examples only – many more scenarios exist but follow the same principles
Table assumes a randomised study where confirmation of CR or PR is not required
For patients with non-target disease only at baseline, only iCR or non-CR/non-PD can be assigned at each TPR but is not shown in the table for ease of presentation

iCR = immune complete response; iPR = immune partial response; iSD = immune stable disease; iUPD = immune unconfirmed progression; iCPD = immune confirmed progression; NL = new lesion; NLT = new lesion target; NLNT = new lesion non target; T = target; TP = timepoint; NA = not applicable; NE = not evaluable / evaluated

Source:

As part of paper presented at the EORTC-NCI-AACR 2016 Meeting (Munich)

Later published as part of Seymour, L., et al., iRECIST: guidelines for response criteria for use in trials testing immunotherapeutics. Lancet Oncol, 2017. Mar; 18(3): e143-e152.

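### The SAP ranks iUPD above iCPD in iRECIST best overall response, so progression confirmed after an iUPD is reported as unconfirmed, contrary to the protocol's own examples

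*SAP*

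**What the plan says.** SAP Section 10.8.3.1 sets the rule in one sentence: the best overall "response is then the best response achieved in order of iCR, iPR, iSD, iUPD, iCPD, NE". It adds that an iUPD may precede a response but an iCPD may not. It then asks for the number and percentage of subjects with each category, iUPD and iCPD included, by cohort and sub-cohort.

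The same section explains how iCPD arises: "they can have progression recorded at a visit but it needs to be confirmed at the subsequent visit for the overall response to be iCPD". That logic carries into Table 6. Its column for subjects without a prior iUPD never returns iCPD; the prior-iUPD column does, for example "Remains iUPD unless iCPD confirmed based on increase in size or number of new lesions previously identified".

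Protocol Section 6.1 has the same sequence, with iCPD as a finding on repeat imaging: "If repeat imaging shows iRECIST confirmed disease progression (iCPD), subjects will discontinue treatment". Protocol Appendix 7 has a table headed "Assigning best overall response for iRECIST", which lists up to five time-point responses and then the resulting best response. Two of its rows read "iUPD iCPD Anything Anything Anything iCPD" and "iUPD iUPD (no iCPD) iCPD Anything Anything iCPD". A further row keeps iUPD as best response where an iUPD is followed only by not-evaluable visits.

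SAP Section 11, which lists departures from the protocol analysis, does not mention the ranking.

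**The concern.** If the best category reached is reported, and confirmed progression is reached only by way of a category ranked above it, confirmed progression can never be the best. Confirmation of progression is the feature that the SAP itself singles out as a key difference between iRECIST and RECIST v1.1, and the summary would not show it.

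Confirmed and unconfirmed progressors would be pooled under iUPD. The two groups differ in this study: under protocol Section 6.1, clinically stable subjects may continue and be re-imaged, while clinically unstable subjects need no confirmatory scan. A reader would also find no best response of iCPD in the response summary, while iPFS and iRECIST DoR count iCPD as an event. The outputs would appear to disagree.

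**Working it through.** The documents give no figure on this point, so there is none to reproduce. The check is one of logic, followed by an enumeration.

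**Step 1: can iCPD occur without an earlier iUPD?** Reading down the ten rows of SAP Table 6, the entries for no prior iUPD are iCR, iPR, iPR, iSD, NA, then iUPD five times. None is iCPD. The time-point table in protocol Appendix 7 is the same.

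**Step 2: apply both rules to the protocol's examples.**

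| Time-point sequence | SAP ranking | Protocol Appendix 7 |
|---|---|---|
| iUPD, iCPD | iUPD | iCPD |
| iUPD, iUPD, iCPD | iUPD | iCPD |
| iUPD, NE, NE, NE, NE | iUPD | iUPD |

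The SAP gives one answer to all three. The protocol separates confirmed from unconfirmed progression.

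**Step 3: enumerate.** Take all sequences of L visits drawn from the six categories, admitting iCPD only after an earlier iUPD, and ignore responses after iCPD.

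- Sequences with no iCPD: 5^L. For L = 5, 3125.
- Sequences whose first iCPD is at visit k: (5^(k−1) − 4^(k−1)) × 6^(L−k). For L = 5 and k = 2 to 5: 216 + 324 + 366 + 369 = 1275. Total admissible: 3125 + 1275 = 4400.
- Of these, sequences with only iUPD or NE before the first iCPD, and at least one iUPD: (2^(k−1) − 1) × 6^(L−k). For L = 5: 216 + 108 + 42 + 15 = 381. These should have a best response of iCPD.

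| Visits L | Admissible | Contain iCPD | Best response iCPD, SAP order | Best response iCPD, iCPD ranked above iUPD |
|---|---|---|---|---|
| 1 | 5 | 0 | 0 | 0 |
| 2 | 26 | 1 | 0 | 1 |
| 3 | 140 | 15 | 0 | 9 |
| 4 | 776 | 151 | 0 | 61 |
| 5 | 4400 | 1275 | 0 | 381 |

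The counts are the same whether or not iCR and iPR must be confirmed. At L = 5 the other 1275 − 381 = 894 sequences with an iCPD had an iCR, iPR or iSD before it, so neither order makes iCPD their best response. With iCPD ranked above iUPD, all three rows of Step 2 match the protocol.

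**Step 4: what else moves?** iORR status and disease control status change in 0 sequences. iRECIST DoR and iPFS (SAP Sections 10.8.3.2 and 10.8.3.4) use the date of the first iCPD, not the best response, so they do not change either. The primary endpoint uses RECIST v1.1.

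**The case against.** The case for leaving the text alone, or treating it as trivial, has several parts.

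- **Scope.** One category split in one descriptive table of an exploratory endpoint is affected. SAP Section 10.1.3 plans no hypothesis tests, and no decision rule uses the split. This stands and limits the weight of the point.
- **The information survives elsewhere.** Listing 16.2.6.3.2 shows iRECIST responses by subject and visit, and iPFS uses the iCPD date. This also stands, but the count that Section 10.8.3.1 asks for would still be wrong.
- **iCPD impossible for anyone, whatever the data.** A reader might infer this, but the documents do not go so far. Table 6 is presented as a set of examples. Protocol Section 6.1 lets clinical deterioration confirm progression with or without radiographic PD, and does not say how that is recorded under iRECIST. An iCPD entered without an earlier iUPD could still come out as iCPD.
- **A printed zero in an iCPD row.** A reader might expect this in Table 14.2.4. Its shell is reused from Table 14.2.1, which has a single PD row and no iCPD row. Section 10.8.3.1 also does not say outright that the category counts are best-response counts.
- **iUPD only when nothing evaluable follows.** The not-evaluable row of Appendix 7 might suggest this, but it is one example. The time-point tables also keep iUPD when a re-scan shows too little further growth. Re-ranking therefore separates confirmed from unconfirmed progression; it does not isolate subjects never re-scanned.
- **Appendix 7 as a ranking.** It gives illustrative sequences, not a ranking, and assumes a randomised study without confirmation of CR or PR. Adopting it whole would conflict with the SAP's confirmation rule. The assumption concerns iCR and iPR, not the progressor rows.

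The SAP's sentence barring iCPD before a response does not rescue the ranking. It discards responses after iCPD; it does not lift iCPD above iUPD.

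**Conclusion.** The ranking is wrong as written. A subject who follows the Table 6 path to confirmed progression with no iCR, iPR or iSD is reported as iUPD, against two explicit protocol examples and with no declared change. On that path the best-response count for iCPD is empty.

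This rests on two assumptions: that recorded time-point responses follow Table 6, and that the category counts in Section 10.8.3.1 are best-response counts. The number of subjects affected cannot be derived from the documents.

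The reach is small: the iUPD/iCPD split in Table 14.2.4 and the best-response column of Listing 16.2.6.4.2. Nothing here supports a claim that response rates, duration of response or progression-free survival are biased. It is worth correcting because the error is clear and the correction is nearly free.

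**What to change.** In SAP Section 10.8.3.1:

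- Change the order to iCR, iPR, iSD, iCPD, iUPD, NE.
- State that iUPD is assigned when progression was never confirmed, whether or not the subject was re-scanned, and no iCR, iPR or iSD was achieved.
- Keep the confirmation requirement for iCR and iPR, and the rule that responses after iCPD do not count. Carry over only the progressor rows of the Appendix 7 table.
- Say that the category counts are best-response counts.

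In the Table 14.2.4 shell, replace the single PD row with separate iUPD and iCPD rows.

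The cost is a few sentences in one SAP section, one derivation change and one shell edit. No new data are needed, and no other endpoint changes.
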